9.1 Primary objective

The primary objective of the trial is to examine the effect of the interventions on the change from baseline in systolic blood pressure 6 months after enrolment. The mean

and SD systolic blood pressure, and the mean and SD change from baseline, at the 6 and 12 month visits will be summarised by treatment arm.

Linear regression will be used to estimate the mean difference, and its 95% confidence interval (CI), between each intervention and SOC (i.e. CBPM vs SOC and eCBPM+ vs. SOC) in the change from baseline at 6 months. The response variable will be systolic blood pressure at 6 months; the model will include treatment arm, clinic, active use of hypertension medication and baseline systolic blood pressure.

In secondary exploratory analyses, we will adjust for baseline values of age, sex, body mass index (BMI), smoking status and HIV. In separate models, we will fit an interaction term between the treatment arm and sub-groups of interest (e.g. sex, age group, co-morbidities) to examine sub-group effect sizes and potential effect modification.

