For participants who cannot be reached to schedule 6 or 12 month visits, a study staff member will attempt a home visit to collect outcome data.

6. Sample size

Based on patient attendance data from the two PHCs in our study in 2020, we estimate that there are over 1000 individuals with uncontrolled hypertension and thus eligible to enrol in the trial. We anticipate mean blood pressure at baseline will be 150/95 mmHg, with a standard deviation (SD) of 19 mmHg, based on previous studies. With 774 participants enrolled (258 per arm), we will have 80% power to detect a 5 mmHg difference between arms in the change of blood pressure from baseline to 6 months, assuming 20% loss to follow-up, a correlation between baseline and follow-up measurements of 0.5, and an alpha of 2.5% to account for multiple testing with comparisons between the SOC and both intervention arms (Table 1).

This same sample size will also give us greater than 80% power to detect an increase in the proportion of participants who achieve BP control (defined by a systolic BP <140 mmHg and diastolic BP <90mm Hg) at 6 months from 30% in the SOC arm to 45% in the interventions arms, or from 40% in the SOC to 56% in the intervention, also allowing for an alpha of 2.5% to account for multiple testing.

Table 1. Differences in change from baseline that can be detected with 80% power

N enrolled per arm	Loss to follow-up	Difference that can be detected (mmHg)	Standard deviation	Correlation between observations	Power
330	20%	5.0	19.0	0.20	80%
258	20%	5.0	19.0	0.50	80%
148	20%	7.5	19.0	0.20	80%
115	20%	7.5	19.0	0.50	80%

7. Definitions and analysis populations

All analyses will be conducted using the intention-to-treat principle, where all randomised participants will be included in the analysis regardless of adherence to the intervention.

All analyses of blood pressure will use the average of the second and third measurement as the blood pressure measurement for that visit. In the primary analyses, participants who are missing any of the three measurements will be considered to be missing blood pressure data for that visit. As a sensitivity analysis, individuals with fewer than three measurements will be included, using the average if there are two, or a single measurement if only one is available.

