For outcomes that are based on data collected at the 6 month visit, the primary analyses will be restricted to participants with the relevant outcome data at 6 months (complete case). For outcomes that use data collected at both the 6 month and the 12 month visits, all participants with outcome data at either visit will be included (see section 10).

Sensitivity analyses will also be conducted where those with missing blood pressure data at a particular visit will be treated as having no change in blood pressure or having uncontrolled blood pressure. The primary analysis will be based on participants with complete blood pressure information; however multiple imputation of missing outcome values may also be used for exploratory analyses (see section 10).

For all outcomes, the primary analysis will be adjusted for clinic and active use of hypertension medication (i.e. the randomisation strata covariates) and blood pressure at baseline. Further, additional analyses adjusted for covariates that are known a

priori to be associated with blood pressure (e.g. age, sex, obesity, co-morbidities), or those that show baseline imbalance, may be conducted to explore the robustness of our results.

An interim analysis may be performed after all participants have completed their 6 month visit, since the primary outcome relates to this time. Data analysis will not begin until the database has been locked and the analysis plan has been signed.

8. Description of the cohort at baseline

In order to assess the comparability of the treatment groups, baseline characteristics of participants will be summarised by arm. Continuous variables will be summarised using means and standard deviations, and categorical variables will be summarised using frequencies and percentages. No formal statistical testing will be done.

Following the CONSORT guidelines, the number of individuals screened, the number who were eligible, and the number enrolled in the trial will be illustrated in a flowchart. Reasons for non-eligibility and non-enrolment will be tabulated. The flow chart will also show the number of participants attending the follow-up visits at 6 and 12 months, and the number withdrawing from the study, by trial arm.

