The baseline characteristics of participants who are included in the analyses at 6 months (primary outcome) and 12 months and those who are not included (either because they withdrew, were lost to follow-up, or missed the relevant visit) will be summarised and compared descriptively.

9. Statistical methods

The statistical methods that will be used to address each study objective are described below. To correct for multiple testing when comparing the two intervention groups with the control group (SOC), we will use the Bonferroni correction with a significance p-value of 0.025

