9.2 Secondary objective

The secondary objective of the trial is to examine the effect of the interventions on the proportion of participants with controlled blood pressure 6 months after enrolment.

The number and proportion of participants with controlled blood pressure (defined as systolic blood pressure <140 mmHg and diastolic blood pressure <90 mmHg) at the 6 and 12-month visits will be tabulated by treatment arm. Logistic regression will be used to estimate the odds ratio (OR) and 95% CI for the effect of each intervention on blood pressure control, compared with SOC. The model will include terms for treatment arm, use of hypertension medication, and clinic [randomisation strata].

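### Age and sex, which the SAP accepts in advance as related to blood pressure, could be pre-specified in the primary SBP model at almost no cost, for an optional and small gain

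*SAP*

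**What the plan says.** SAP section 7 sets a general rule: the primary analysis of every outcome adjusts for the two randomisation strata (clinic and current antihypertensive use) and for baseline blood pressure. It then allows, without requiring, further analyses adjusted for covariates known a "priori to be associated with blood pressure (e.g. age, sex, obesity, co-morbidities", or for covariates found unbalanced at baseline.

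Section 9.1 models 6-month SBP on arm, clinic, antihypertensive use and baseline SBP. Age and sex come in only afterwards: "In secondary exploratory analyses, we will adjust for baseline values of age, sex, body mass index (BMI), smoking status and HIV".

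Section 9.2, on blood pressure control, reads: "The model will include terms for treatment arm, use of hypertension medication, and clinic [randomisation strata". It has no age, no sex and no baseline blood pressure. For this outcome, age and sex adjustment rests on the optional clause in section 7.

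Section 10 uses sex and age (60 years and over, or under 60) as subgroups and puts both in the optional imputation model. The protocol's Aim 2 Analysis Plan adjusts the SBP model for baseline SBP only. Neither document gives a reason for leaving age and sex out of the main models.

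**The concern.** If the plan already accepts two baseline variables as prognostic, will hold them for every participant and can add them without changing what the linear model estimates, the usual choice is to pre-specify them. Two things are at stake in 9.1.

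- **Precision.** Any 6-month SBP variance that age and sex explain beyond baseline SBP would reduce the standard error of the arm difference. The design has little slack: it sits at 80% power with baseline SBP already credited.
- **Discretion.** Section 7 leaves open whether further adjusted analyses are run, and one trigger is observed imbalance. If age or sex is unbalanced by chance, readers would have a primary estimate without them and an exploratory one with them. Putting both in the primary model settles beforehand which estimate leads.

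In 9.2 the larger gap is different: the stated model omits the baseline blood pressure term that section 7 prescribes for all outcomes.

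**Working it through.** **Inputs.** From SAP section 6: an enrolment of 258 in each arm, 774 in all; the target, "we will have 80% power to detect a 5 mmHg difference between arms in the change of blood pressure from baseline to 6 months"; the spread, "with a standard deviation (SD) of 19 mmHg, based on previous studies"; and, for attrition and correlation, "assuming 20% loss to follow-up, a correlation between baseline and follow-up measurements of 0.5". From section 9: "we will use the Bonferroni correction with a significance p-value of 0.025". The SAP does not say whether the test is one- or two-sided; I take it as two-sided. The share r of the remaining 6-month SBP variance that age and sex explain, given the terms already in the model, is not in the documents. It is an assumption, shown as a range that includes zero.

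**Step 1: reproduce the plan.** Residual variance after baseline SBP is 19² × (1 − 0.5²) = 270.75, an SD of 16.45.

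n per arm = 2 × 270.75 × (2.2414 + 0.8416)² / 5² = 205.9, so 206 completers. Then 206 / 0.8 = 257.5, so 258 enrolled, as stated. The other rows of SAP Table 1 (330, 148, 115) reproduce in the same way. A change-score SD would give 344 and a two-sided alpha of 0.05 would give 214. The plan therefore credits baseline SBP and nothing more.

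**Step 2: add age and sex to 9.1.** SE = √(2 × 270.75 × (1 − r) / 206). Power = Φ(5/SE − 2.2414). Half-width = 1.96 × SE.

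| r (assumed) | SE (mmHg) | 95% CI half-width | Power at 5 mmHg |
|---|---|---|---|
| 0% | 1.621 | 3.18 | 80.0% |
| 1% | 1.613 | 3.16 | 80.5% |
| 3% | 1.597 | 3.13 | 81.3% |
| 5% | 1.580 | 3.10 | 82.2% |

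In enrolment terms, 774 × r/(1 − r) is 0, 8, 24 or 41 participants. A more generous r of 10% would give SE 1.538 and power 84.4%.

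For scale, without baseline SBP (SD 19, 206 per arm) power would be 66.6%. Baseline SBP raises it to 80.0%, so the large gain is already in the model.

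**Step 3: section 9.2.** The two-proportion formula at 206 per arm and alpha 0.025 gives 82.0% power (30% v 45%) and 84.7% (40% v 56%), consistent with the SAP. The effect of covariates was simulated by logistic regression for 30% v 45%: 1,500 runs per setting, a latent normal blood pressure, baseline correlation 0.5, one continuous index standing for age and sex, and no strata terms. Each cell shows power and the SE of the log odds ratio.

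| r (assumed) | Arm only | + age/sex | + baseline BP | + both |
|---|---|---|---|---|
| 2% | 81.3%, 0.207 | 82.5%, 0.209 | 88.2%, 0.229 | 88.4%, 0.231 |
| 5% | 82.7%, 0.207 | 84.2%, 0.211 | 88.5%, 0.229 | 90.1%, 0.233 |
| 10% | 80.3%, 0.207 | 81.9%, 0.213 | 86.0%, 0.229 | 88.4%, 0.237 |

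Monte Carlo error is about 1 point; comparisons within a row use the same simulated data. Baseline blood pressure adds about 6 to 7 points. Age and sex alone add about 1 to 2, and 0.2 to 2.4 on top of baseline blood pressure. The SE rises each time because the odds ratio becomes conditional on more covariates and moves away from 1. The benefit is power, not a narrower interval.

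**The case against.** The strongest reply is that this is a preference, not a defect. The 9.1 model is a pre-specified, valid analysis of covariance with both strata and baseline SBP, and it meets its stated power. The adjusted SBP analysis is firmly planned, though as exploratory, and section 7 permits one for blood pressure control. All of that stands, which is why the point is only an optional improvement.

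It also stands that a relation with blood pressure is not the same as predicting 6-month SBP once baseline SBP, clinic and treatment are known. Only the latter buys precision, and the gain may be close to zero.

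The choice of two covariates is a judgement too. Section 7 gives obesity and co-morbidities the same status. Age and sex are the simplest to fix in advance, and the subgroups need them anyway. HIV status is self-reported, but nothing in the documents says that BMI or smoking will be incomplete.

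A reader might infer more than the documents support:

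- That randomisation leaves age and sex unbalanced. It balances them in expectation; they are simply not stratification factors, and large chance imbalance is unlikely with 258 per arm.
- That the complete-case analysis is biased without them. Conditioning on age and sex would let missingness depend on them, but nothing in the documents shows that it does. The protocol expects no difference in loss between arms.

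What the reply does not answer is why the decision should stay open, when pre-specifying it costs two degrees of freedom.

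**Conclusion.** The point holds as an optional, low-priority improvement to 9.1. Age and sex are treated as prognostic in section 7 but kept out of the primary SBP model. Adding them would leave the linear estimand unchanged, and power at 5 mmHg would move from 80.0% to between 80.0% and 82.2% for an assumed r of 0% to 5%. This rests on the SAP's own design values, a two-sided alpha of 0.025 and 206 completers per arm. The advance decision on which estimate leads is worth having even if r is zero.

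It would be tempting to say that the plan gives up precision in both models for nothing. The documents do not support that: they give no value for r, and in the logistic model added covariates widen the interval for the log odds ratio while raising power slightly.

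In 9.2 the matter to reconcile first is baseline blood pressure, which section 7 requires and 9.2 leaves out. Under the simulation's assumptions it is worth several times what age and sex add alone.

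**What to change.** - **Section 9.1:** add age (continuous) and sex to the primary model alongside arm, clinic, antihypertensive use and baseline SBP. Keep BMI, smoking and HIV in the exploratory model.
- **Section 9.2:** first add baseline blood pressure, so that the model agrees with section 7. Age and sex may be added as well; if they are, say that the odds ratio is conditional on the added covariates.
- **Timing:** make the change in a dated SAP amendment before data are examined by arm. If that point has already passed, which the documents do not show, leave the 9.1 primary model as signed and report the age- and sex-adjusted estimate as supportive.

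The cost is a sentence in each section. It needs no new data and uses two degrees of freedom among 3 × 206 = 618 expected completers.

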9.2 Secondary objective

The secondary objective of the trial is to examine the effect of the interventions on the proportion of participants with controlled blood pressure 6 months after enrolment.

The number and proportion of participants with controlled blood pressure (defined as systolic blood pressure <140 mmHg and diastolic blood pressure <90 mmHg) at the 6 and 12-month visits will be tabulated by treatment arm. Logistic regression will be used to estimate the odds ratio (OR) and 95% CI for the effect of each intervention on blood pressure control, compared with SOC. The model will include terms for treatment arm, use of hypertension medication, and clinic [randomisation strata].

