We will summarize participant sociodemographic and clinical characteristics at baseline in all three arms. We will use linear regression to estimate the difference between arms, and its 95% confidence interval (CI), in systolic blood pressure at 6 months, adjusted for baseline systolic BP. We will use logistic regression to estimate odds ratios (OR) and 95% CIs for the impact of the intervention on the proportion of participants who achieve blood pressure control (<140/90) at 6 months.

Characteristics of individuals who are lost to follow-up will be tabulated by study arm. Since study nurses will visit all participants at home to measure blood pressure at 6 and 12 months, we do not expect there to be differential loss to follow-up between arms. In the primary analyses, participants with missing data at 6 months will be excluded. In sensitivity analyses, those with missing measurements will be considered to have no change in systolic BP and uncontrolled BP. Missing values may also be imputed using multiple imputation.

In pre-planned secondary analyses, we will fit regression models stratified by sex (to assess for sex as a biologic variable), age strata, socioeconomic status and baseline co-morbidities (i.e. obesity and HIV) to determine sub-group effect sizes and test the significance of an interaction term between sub-groups and the intervention to assess for effect modification.

A detailed statistical analysis plan will be prepared before the data are examined by treatment arm.

M. Risks, Protection from Risks and Benefits to Study Participation in Aim 2

a. Risks and Protections

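### SAP section 7 adjusts every outcome for baseline blood pressure, but the section 9.2 model for blood pressure control leaves it out, and nothing says which governs

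*SAP*

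**What the plan says.** SAP section 7 (Definitions and analysis populations) sets a general rule: "For all outcomes, the primary analysis will be adjusted for clinic and active use of hypertension medication". It continues: "i.e. the randomisation strata covariates) and blood pressure at baseline". The strata and baseline pressure are therefore separate items, and both are required.

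Section 9.1, for systolic blood pressure (SBP), follows the rule: "the model will include treatment arm, clinic, active use of hypertension medication and baseline systolic blood pressure".

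Section 9.2, for blood pressure control, does not: "The model will include terms for treatment arm, use of hypertension medication, and clinic [randomisation strata". It carries over the strata and drops baseline pressure.

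Section 9 introduces these models only with "The statistical methods that will be used to address each study objective are described below". Protocol section L (Aim 2 Analysis Plan) adjusts the SBP model for baseline SBP but names no covariates for control: "We will use logistic regression to estimate odds ratios (OR) and 95% CIs for the impact of the intervention on the proportion of participants".

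**The concern.** Section 7 has no exception clause, and section 9 does not say that it overrides section 7. An analyst could fit the control model with or without baseline pressure and cite signed SAP text either way.

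This matters more for a logistic model than for a linear one. Odds ratios are non-collapsible: adding a covariate that predicts the outcome changes the quantity being estimated as well as the precision. Each model controls its own error rate. Freedom to report the more favourable one does not, and removing that freedom is the purpose of pre-specification. Allocation is open to participants and clinic staff, and section 7 allows an early look: "An interim analysis may be performed after all participants have completed their 6 month visit". The choice should be closed before then.

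**Working it through.** **Inputs from SAP section 6.** 258 enrolled per arm; 20% loss to follow-up; SBP SD 19 mmHg; baseline to follow-up correlation 0.5 (0.2 also tabulated); alpha 0.025 per comparison, taken as two-sided because that reproduces the plan's figures; control rates 30% vs 45% and 40% vs 56%; mean baseline pressure 150/95 mmHg.

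**Step 1: reproduce the sample size.** With adjustment for baseline SBP, n = 2 × 19² × (1 − 0.5²) × (2.2414 + 0.8416)² / 5² = 205.9, so 206 evaluable per arm. 206 / 0.8 = 257.5, so 258 enrolled. This matches the SAP.

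**Step 2: reproduce the power for control.** The SAP claims "greater than 80% power to detect an increase in the proportion of participants who achieve BP control". Without baseline pressure, using the pooled-variance two-proportion formula with n = 206 and p̄ the mean of the two rates:

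z = [(p₁ − p₀)√n − 2.2414 √(2p̄(1 − p̄))] / √(p₀(1 − p₀) + p₁(1 − p₁))

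- 30% vs 45%: z = (2.153 − 1.535) / 0.676 = 0.914, power 82.0%.
- 40% vs 56%: z = (2.296 − 1.584) / 0.697 = 1.022, power 84.7%.

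The marginal odds ratio is 1.91 in both. The SAP's claim holds.

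**Step 3: compare the two models by simulation.** Model A has arm and strata, as in 9.2. Model S adds continuous baseline SBP. Each scenario has 8,000 trials (standard error about 0.4 points on power, 0.3 on paired differences). The documents do not give the following, so they are assumed: diastolic (DBP) SD 12; SBP–DBP correlation 0.6; the same baseline to follow-up correlation for DBP as for SBP; two balanced binary strata shifting follow-up pressure by 0.2 and 0.1 SD. The truncated runs keep only people with SBP >140 or DBP >90, from a source population solved so that those enrolled match 150/95 and SD 19/12.

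Power (%), model A → model S:

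| Correlation | Entry truncation | 30% vs 45% | 40% vs 56% |
|---|---|---|---|
| 0.5 | yes | 82.5 → 84.3 | 85.0 → 87.3 |
| 0.5 | no | 82.5 → 87.0 | 84.7 → 88.7 |
| 0.2 | yes | 82.7 → 82.9 | 84.5 → 84.9 |
| 0.2 | no | 82.7 → 83.1 | 85.0 → 85.4 |

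At correlation 0.5 the odds ratio moves from 1.93–1.94 to 2.00–2.12, and the verdict differs in 4.2% to 7.7% of trials. At 0.2 the adjusted odds ratio is 1.95–1.97 and the verdict differs in 1.7% to 2.5%. The standard error of the log odds ratio is 0.202–0.210 under A and 0.204–0.225 under S, so the power gain comes from a larger odds ratio and not from a narrower interval.

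**Step 4: type I error.** With 30% control in both arms and 20,000 trials per scenario (standard error about 0.12 points), rejection rates (%) are:

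| Correlation | Entry truncation | A | S | Either |
|---|---|---|---|---|
| 0.5 | yes | 2.70 | 2.60 | 3.23 |
| 0.5 | no | 2.54 | 2.62 | 3.38 |
| 0.2 | yes | 2.62 | 2.62 | 2.86 |
| 0.2 | no | 2.64 | 2.67 | 3.00 |

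**Sensitivity.** Without truncation, at correlation 0.5, an SBP–DBP correlation of 0.4 gives a gain of 3.2 to 4.1 points, and 0.8 gives 5.4 to 5.8 points. Adding baseline DBP to model S, across both sets of runs at 0.5, gives a total gain over A of 3.3 to 5.7 points and an odds ratio of 2.06–2.18. These runs illustrate the size of the effect. They are not bounds.

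**The case against.** The best reply is that the specific section governs. Section 7 deals with definitions and populations, while section 9 is where models are specified. The drafting is also consistent: both SBP models (9.1 and section 10) name baseline SBP, and none of the three logistic models (9.2, 9.3, section 10) does. The protocol shows the same split. This may be a loosely worded general clause and not two intended models. That is a fair reading of intent, but no rule of precedence is written and section 7 says all outcomes. The reply shows that the conflict could be settled either way, not that it has been settled.

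Three narrower points carry weight.

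- The untruncated runs include people the trial would not enrol: under the assumed values, about 19% would have neither SBP >140 nor DBP >90. The truncated figures are the better guide, so the lower ends of the ranges should be given more weight.
- Section 7 does not say whether baseline blood pressure means systolic, diastolic or both. Choosing SBP is a judgement, made to match 9.1.
- Naming the model with the larger odds ratio as primary after the data have been seen would be weak. It is defensible only if both results are reported and the timing is disclosed.

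**Conclusion.** The concern holds. The SAP gives two covariate sets for its only secondary outcome and no way to choose between them. The conflict is a matter of text and does not depend on the simulation.

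The practical effect is minor to moderate. If the correlation is near 0.5, the choice is worth about 2 points of power with entry truncation, changes some verdicts, and allows about 3.2% type I error instead of 2.5% if the better result is picked. If it is near 0.2, little changes. The sizes rest on the assumed DBP spread, SBP–DBP correlation and strata effects. The sample size, the stated power and the primary outcome all stand.

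The 9.3 model for retention in care also omits baseline pressure, but the conflict there is only arguable because the SAP lists retention as a safety measure. The section 10 control model is exploratory and does not contradict section 7.

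**What to change.** Amend 9.2 so that the logistic model contains arm, clinic, antihypertensive use at enrolment and baseline SBP as a continuous covariate, the same set as 9.1. State in section 7 which baseline pressure is meant. Baseline DBP could be added because control is defined on both pressures, but this is optional. Add a sentence to 9.3 saying whether the section 7 rule applies to retention. Adding baseline SBP to the section 10 control model is optional, for consistency with its linear counterpart.

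Make the change before outcomes are examined by arm, including before the optional 6-month analysis. If that point has passed, name the section 7 model as primary because it is the rule written for all outcomes, report both models together, and disclose when the choice was made.

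The cost is a few words, using data already collected. The odds ratio becomes conditional on baseline pressure, and a participant without all three enrolment readings drops out of the 9.2 model, as already happens in 9.1.

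Restricting the section 7 clause to the SBP analyses would also remove the conflict. At correlation 0.5 it would give up about 2 to 4.5 points of power.
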